6.12.2.2 Liver Function Abnormality

A summary of liver function abnormalities by analysis period will be provided. Any subject with at least 1 of the following liver function abnormalities will be summarized:

- Alanine aminotransferase (ALT) >2x and <=3x upper limit of normal (ULN)
- ALT >3x and <=5x ULN;
- ALT >5x and <=10x ULN;
- ALT >10x ULN
- Aspartate aminotransferase (AST) >2x and <=3x ULN;
- AST >3x and <=5x ULN;
- AST >5x and <=10x ULN;
- AST >10x ULN
- Total bilirubin >2x and <=3x ULN;
- Total bilirubin >3x ULN

In addition, a table will summarize the occurrence of events that satisfy the following criteria of liver injury:

- (ALT or AST >3x ULN and <=5x ULN) and total bilirubin >2x ULN;
- (ALT or AST >5x ULN and <=10x ULN) and total bilirubin >2x ULN;
- ALT or AST >10x ULN and total bilirubin >2x ULN

6.12.2.3 Other Laboratory Safety Endpoints

Descriptive statistics for laboratory values (in US conventional and SI units) and changes from baseline at each analysis visit will be summarized for the following laboratory parameters collected in the study including but not limited to the following:

- Complete blood count (CBC): Hb, hematocrit, red blood cell (RBC), MCV, MCH, MCHC, platelets, RDW, white blood cell (WBC) with differential (neutrophils, lymphocytes, monocytes, eosinophils, basophils), reticulocyte count
- Serum chemistry: sodium, potassium, bicarbonate, chloride, calcium, magnesium, phosphorus, glucose, creatinine, BUN, CPK, uric acid, albumin, total protein
- Liver function tests: Total bilirubin, ALP, ALT/SGPT, AST/SGOT, LDH
- Iron indices: Iron, ferritin, TSAT, TIBC
- Lipid Profile: Total cholesterol, LDL, HDL, Triglycerides
- CRP
- EPO

A summary of the number and percentage of subjects experiencing clinically significant values for the following parameter definitions will be presented by analysis period:

- Potassium >6.0 mmol/L

6.12.3 Physical Examination

With only the Date of Assessment collected (if performed) on the physical examination in the eCRF, no output is planned for it. If there are clinically significant abnormal findings, details can be found in the listings of medical history or adverse event.

6.12.4 Vital Signs

For blood pressure, a total of 2 measurements at intervals of at least 2 minutes will be performed. For change from baseline related summaries, the average of the blood pressure within the same visit will be calculated as the results for the visit. For the individual value criteria, an individual result will be used instead of the average.

Descriptive statistics for vital signs (systolic blood pressure, diastolic blood pressure, heart rate, respiratory rate, temperature, weight (pre-dialysis and post-dialysis)) and their change from baseline will be provided by each analysis visit.

The number and percentage of subjects experiencing the following findings by analysis periods will be provided:

- SBP ≥ 180 mmHg
- SBP ≥ 160 mmHg
- DBP ≥ 110 mmHg
- SBP or DBP: Increase from baseline ≥ 20 mmHg

- Meet Both/Either Criteria
 - SBP ≥ 160 mmHg and increase from baseline ≥ 20 mmHg
 - DBP ≥ 110 mmHg and increase from baseline ≥ 20 mmHg

This figure displays a 2D grayscale heatmap of a face, possibly a portrait of a man. The image is significantly blurred, resulting in a dark, indistinct blob-like appearance. A 3x3 grid of small black squares is overlaid on the image, centered on the face area. The background is white.

Statistical Analysis Plan
Protocol No. AKB-6548-CI-0039

Akebia Therapeutics, Inc.

The figure consists of a 10x10 grid of black bars on a white background. The bars are arranged in a pattern where they are longer in the first and last columns and shorter in the middle columns. The height of the bars in the first column decreases from top to bottom. The height of the bars in the last column increases from top to bottom. The bars in the middle columns are consistently short.

Statistical Analysis Plan Protocol No. AKB-6548-CI-0039

Akebia Therapeutics, Inc.

k	n	Value
2	2	100
3	3	100
3	6	100
4	4	100
4	12	100
4	24	100
5	5	100
5	10	100
5	20	100
5	40	100

6.14 SUBGROUP ANALYSES

The same analyses of the primary efficacy endpoint and secondary efficacy endpoint will also be performed for subgroups based on the following. Subgroup analyses will be performed only if the total number of outcomes in a stratum, combined over the two treatment groups, is at least 30.

- Dialysis organization [USRC (U.S. Renal Care), ARCRS (American Renal Clinical Research Services), Frenova (Frenova Renal Research)]
 - Age (<65 years, \geq 65 years)
 - Sex (Male, Female)
 - Race (White, Black, All others)
 - Baseline Hb (<10.0 g/dL, \geq 10.0 g/dL)

7. CHANGES TO PROTOCOL-PLANNED ANALYSES

Removed the hierarchical testing scheme for both primary and secondary efficacy endpoints. Treatment comparisons will be performed between vadadustat (combining the 2 randomized groups with starting dose of 600mg and 900mg) and Mircera groups. Subjects in the vadadustat starting dose groups of 600 mg or 900 mg TIW will have their doses adjusted to maintain Hb levels of 10.0 to 11.0 g/dL following the protocol's dosing algorithm. The subgroup analysis with different starting dose with vadadustat vs. Mircera will be considered as exploratory analyses.

The figure consists of two rows of four bar charts each. The top row is labeled 'Publications' and the bottom row is labeled 'Citations'. Each bar chart has four bars representing different metrics: 'Publications' (black), 'Citations' (white), 'Publications' (black), and 'Citations' (white). The groups are labeled A, B, C, and D.

Group	Publications 1	Citations 1	Publications 2	Citations 2
A	100	100	100	100
B	100	100	100	100
C	100	100	100	100
D	100	100	100	100

[figure not shown]
Statistical Analysis Plan

Akebia Therapeutics, Inc.

zardratio 'Cox proportional hazard' TRT;

RUN;

[REDACTED]

[REDACTED]

[REDACTED]

[REDACTED]

[REDACTED]

[REDACTED]

[REDACTED]

For efficacy endpoints of having average Hb value in the target range in Weeks 20-26 and Weeks 46-52, these endpoints are binary; they will be analysed according to the Mantel-Haenszel estimate of stratified risk differences. These binary outcome measures will be computed from the continuous imputed data which will serve as the input data set for the computation of the estimate of risk difference. The code for this analysis is provided as below.

[REDACTED]

[REDACTED]

[REDACTED]

[REDACTED]

[REDACTED]

[REDACTED]

[REDACTED]

B.3. Tipping Point Sensitivity Analysis for Missing Data

This multiple imputation model for the primary efficacy model described above assumes that data in both treatment arms are missing at random (MAR) and would therefore follow the trend of observed data. The tipping point analysis assesses the effect of potential deviations from this assumption and explores the consequences of assuming that data in the vadadustat arm are missing not at random (MNAR) (i.e., subjects in the vadadustat arm with missing outcome are assumed to have a lower Hb values than subjects in the Mircera arm). The specific steps are as follows:

1. The missing information on Hb in the vadadustat arm will be multiply imputed using a shift parameter S applied to lower the mean Hb values in that arm. Missing data in the Mircera arm will continue to be imputed assuming MAR, using the same code as for the primary efficacy analysis subset to the Mircera arm.
 2. The multiply imputed data will be analysed using PROC MIANALYZE to obtain an estimated treatment effect and its associated 95% CI.
 3. Steps 1 and 2 will then be repeated. The shift parameter S starts from 0, which corresponds to the primary efficacy analysis with no shift effect and decreased by 0.1 in each step until the analysis reaches the “tipping point” (i.e., lower limit of CI < -0.75), the point at which the effect of vadadustat is no longer noninferior to that of Mircera. The more the tipping point diverges from the observed data, the more robust the conclusion based on primary efficacy analysis.
-

B.4. Random Seed Specification

Assigned seeds in proc mi for multiple imputations will be generated randomly from a master seed 65480039. The SAS code and the generated seed numbers are listed below.

Statistical Analysis Plan
Protocol No. AKB-6548-CI-0039

Akebia Therapeutics, Inc.

Statistical Analysis Plan
Protocol No. AKB-6548-CI-0039

Akebia Therapeutics, Inc.

Statistical Analysis Plan
Protocol No. AKB-6548-CI-0039

Akebia Therapeutics, Inc.

Statistical Analysis Plan
Protocol No. AKB-6548-CI-0039

Akebia Therapeutics, Inc.

[figure not shown]
Statistical Analysis Plan
Protocol No. AKB-6548-CI-0039

Akebia Therapeutics, Inc.

Statistical Analysis Plan
Protocol No. AKB-6548-CI-0039

[figure not shown]
Akebia Therapeutics, Inc.

Statistical Analysis Plan
Protocol No. AKB-6548-CI-0039

[figure not shown]
Akebia Therapeutics, Inc.

Statistical Analysis Plan
Protocol No. AKB-6548-CI-0039

[figure not shown]
Akebia Therapeutics, Inc.

Statistical Analysis Plan
Protocol No. AKB-6548-CI-0039

Akebia Therapeutics, Inc.

Statistical Analysis Plan
Protocol No. AKB-6548-CI-0039

Akebia Therapeutics, Inc.

Appendix E. Adverse Events of Special Interest (AESI)

The following items will be presented as AESI.

- Worsening of Hypertension: Hypertension MedDRA SMQ Narrow
- Hepatotoxicity: Drug related hepatic disorders Comprehensive SMQ broad
- Pulmonary Hypertension: Pulmonary Hypertension SMQ narrow
- Adrenal disorder: high-level group term (HLGT) Adrenal gland disorders not elsewhere classified (NEC), high-level term (HLT) Adrenal cortex tests
- Malignancies: Malignant or unspecified tumors MedDRA SMQ broad
- Congestive heart failure: Cardiac failure MedDRA SMQ Narrow
- Adverse event preferred terms used in key queries from FDA briefing document for Roxadustat are listed below:

Medical Topic	PT Term
Thrombosis	Cerebral infarction
	Embolic cerebral infarction
	Ischaemic stroke
	Cerebellar infarction
	Lacunar stroke
	Embolic stroke
	Brain stem stroke
	Lacunar infarction
	Thrombosis in device
	Arteriovenous fistula thrombosis
	Arteriovenous graft thrombosis
	Vascular access site thrombosis
	Vascular graft thrombosis
	Graft thrombosis
	Shunt thrombosis
	Acute myocardial infarction
	Myocardial infarction
	Deep vein thrombosis
	Thrombosis
	Atrial thrombosis
	Peripheral artery thrombosis
	Subclavian vein thrombosis
	Brachiocephalic vein thrombosis

Medical Topic	PT Term
	Subclavian artery thrombosis
	Vena cava thrombosis
	Thrombophlebitis superficial
	Arterial thrombosis
	Thrombophlebitis
	Jugular vein thrombosis
	Venous thrombosis
	Pelvic venous thrombosis
	Venous thrombosis limb
	Cardiac ventricular thrombosis
	Intracardiac thrombus
Device/shunt thrombosis/occlusion/malfunction/Stenosis	Thrombosis in device
	Arteriovenous fistula thrombosis
	Arteriovenous graft thrombosis
	Vascular access site thrombosis
	Vascular graft thrombosis
	Medical device site thrombosis
	Device occlusion
	Arteriovenous fistula occlusion
	Vascular access site occlusion
	Vascular access complication
	Vascular access malfunction
	Arteriovenous graft site stenosis
	Shunt occlusion
	Shunt malfunction
	Vascular graft stenosis
	Anastomotic stenosis
	Vascular access site complication
	Vascular graft occlusion
Device/shunt thrombosis	Thrombosis in device
	Arteriovenous fistula thrombosis
	Arteriovenous graft thrombosis
	Vascular access site thrombosis
	Vascular graft thrombosis

Medical Topic	PT Term
	Graft thrombosis
	Shunt thrombosis
	Medical device site thrombosis
	Device related thrombosis
	Injection site thrombosis
Seizure FDA	Epilepsy
	Epileptic encephalopathy
	Seizure
	Generalised tonic-clonic seizure
	Idiopathic partial epilepsy
	Partial seizures
	Tonic convulsion
Stroke	Cerebral infarction
	Embolic cerebral infarction
	Ischaemic stroke
	Cerebellar infarction
	Lacunar stroke
	Embolic stroke
	Brain stem stroke
	Lacunar infarction
	Cerebrovascular accident
	Haemorrhagic stroke
	Brain stem haemorrhage
Sepsis/septic shock	Device related sepsis
	Enterococcal sepsis
	Sepsis
	Urosepsis
	Streptococcal sepsis
	Pseudomonal sepsis
	Staphylococcal sepsis
	Septic shock
	Sepsis syndrome
	Biliary sepsis
	Bacterial sepsis

Medical Topic	PT Term
	Fungal sepsis
	Citrobacter sepsis
	Listeria sepsis
	Abdominal sepsis
	Septic encephalopathy
	Escherichia sepsis

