6.2 Exclusion Criteria

Subjects must not meet any of the following exclusion criteria:

1. Anemia due to a cause other than CKD (e.g., sickle cell disease, myelodysplastic syndromes, bone marrow fibrosis, hematologic malignancy, myeloma, hemolytic anemia, thalassemia, or pure red cell aplasia).
2. Clinically meaningful bleeding event in opinion of investigator within 8 weeks prior to Baseline.
3. RBC transfusion within 8 weeks prior to Baseline.
4. Having received any doses of darbepoetin alfa (Aranesp[®]) within 4 weeks prior to Baseline.
5. Having received any doses of epoetin alfa (Epogen[®]) within 1 week prior to Baseline.
6. Anticipated to discontinue hemodialysis during the study.
7. Judged by the Investigator that the subject is likely to need rescue therapy (ESA administration or RBC transfusion) immediately after enrollment in the study.
8. History of chronic liver disease (e.g., chronic infectious hepatitis, chronic autoimmune liver disease, cirrhosis or fibrosis of the liver).
9. Aspartate aminotransferase (AST)/serum glutamic oxaloacetic transaminase (SGOT), alanine aminotransferase (ALT)/serum glutamic pyruvic transaminase (SGPT), or total bilirubin >2 x upper limit of normal (ULN) during Screening. Subjects with a history of Gilbert's syndrome are not excluded.
10. Current uncontrolled hypertension as determined by the Investigator that would contraindicate the use of an ESA.
11. Acute coronary syndrome (hospitalization for unstable angina or myocardial infarction), surgical or percutaneous intervention for coronary, cerebrovascular or peripheral artery disease (aortic or lower extremity), surgical or percutaneous valvular replacement or repair, sustained ventricular tachycardia, hospitalization for HF or New York Heart Association Class IV HF, or stroke within 12 weeks prior to or during Screening.
12. History of new, active or recurrent malignancy within 2 years prior to and during Screening or currently receiving treatment or suppressive therapy for cancer. Subjects with treated basal cell carcinoma of skin, curatively resected squamous cell carcinoma of

skin, or treated cervical carcinoma in situ are not excluded.

13. History of deep vein thrombosis or pulmonary embolism within 12 weeks prior to or during Screening.
14. History of hemosiderosis or hemochromatosis.
15. History of prior organ transplantation (subjects with a history of failed kidney transplant or corneal transplants are not excluded).

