9.11.8 Events of Special Interest

The following are considered to be AESIs for this study:

- malignancy including renal cell carcinoma (see [Section 9.11.1.2](#))
- elevation in ALT or AST >3 x ULN (see [Section 9.11.1.2](#))
- hepatotoxicity
- worsening of hypertension
- pulmonary hypertension
- thrombotic events
- congestive HF
- adrenal disorders

Reporting and classification of these events as SAEs (see [Section 9.11.1.2](#)) will be as per usual practice.

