6.12.1 Adverse Events

A treatment-emergent adverse event (TEAE) is one that begins or worsens after treatment initiation. TEAEs will be summarized using the number and percentage of subjects with TEAEs for all subjects in the safety population.

All AEs will be coded by MedDRA. The MedDRA version used for reporting this study will be described in a footnote on AE related outputs. TEAEs will be summarized by SOC and PT for each treatment group. All TEAE summaries will provide the number of subjects reporting at least 1 TEAE. TEAE summaries will be ordered by decreasing pooled percentage for SOC, and PT within SOC.

An overall summary table will show number of subjects with at least 1 of each of the following:

- TEAE
- Drug-related TEAE
- Severe TEAE
- Treatment-emergent SAE
- Drug-related treatment-emergent SAE
- TEAE leading to withdrawal of study drug
- Drug-related TEAE leading to withdrawal of study drug
- Fatal TEAE
- All Deaths: Any deaths reported during the study no matter whether deaths are caused by TEAEs

Summaries by SOC and PT will be provided for the following types of TEAEs:

- TEAE
- TEAE by severity
- Drug-related TEAEs (including all categories for relationship to study medication other than “Unrelated”, as determined by the investigator)
- Treatment-emergent serious adverse event (SAE)

-
- Drug-related treatment-emergent SAE
 - TEAEs leading to withdrawal of study drug
 - Drug-related TEAE leading to withdrawal of study drug
 - Fatal TEAE
 - Adverse events of special interest (AESI) listed on [Appendix E](#)

A summary by treatment group and PT will be presented for TEAEs reported by at least 5% of subjects in either treatment group.

TEAEs will be summarized by 1) worst severity, and 2) worst causality by SOC and PT. For each subject and each PT, the worst severity recorded will be used in the by-severity summaries. Similarly, the worst causality (most related to treatment) attributed will be used in the by-causality summaries. If severity or causality is missing, data will be imputed to the worst category.

Treatment-emergent SAEs and deaths will be summarized by treatment group and overall, including the number and percentage for subject with Treatment-emergent SAEs, number of deaths (all causes, resulting from adverse events). Summary by SOC and PT will include subjects affected by Treatment-emergent SAEs, occurrence (all, causally related to treatment), number of death (all causes), and deaths causally related to treatment.

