A by-subject listing of all TEAEs will be provided. This listing will be presented by treatment group and will include center, subject identifier, age, sex, race, AE (SOC, PT, and verbatim term), study day of onset, study day of resolution, duration, severity, seriousness, relationship to the study medication, action taken, outcome and causality.

A by-subject listing of all Aes happening before first dose date will be provided.

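### The SAP's Thrombosis term list, the evident match for the protocol's thrombotic-events AESI, leaves out pulmonary embolism

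*SAP*

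**What the plan says.** Protocol section 9.11.8 names eight AESIs. One is "thrombotic events". Section 3.5.3 repeats it, and neither place gives terms or a query.

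SAP section 6.12.1 includes "Adverse events of special interest (AESI) listed on" Appendix E among its summaries by system organ class and preferred term. Appendix E defines six of the eight protocol AESIs by a MedDRA query or group term: hypertension, hepatotoxicity, pulmonary hypertension, adrenal disorder, malignancies and congestive heart failure. Transaminase elevation is handled in section 6.12.2.2: "A summary of liver function abnormalities by analysis period will be provided".

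The last bullet of Appendix E reads "Adverse event preferred terms used in key queries from FDA briefing document for Roxadustat are listed below". Six topic lists follow, and the first is headed Thrombosis. It includes "Deep vein thrombosis".

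Pulmonary embolism is named in the documents only in exclusion criterion 13 (protocol section 6.2 and the synopsis), which begins "History of deep vein thrombosis or pulmonary embolism within 12 weeks".

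**The concern.** An explicit preferred-term list counts what is on it and nothing else. The Thrombosis list is broad: it covers arterial, venous, cardiac, cerebral and vascular-access events. A reader of a thrombotic AESI row built on it would reasonably take pulmonary embolism to be inside. It is not, while deep vein thrombosis is.

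The AESI matters in this protocol. Section 3.5.1 reports fibrin thrombi in multiple organs in nonclinical studies. Table 2 shows arteriovenous fistula thrombosis in 6.0% of vadadustat subjects against 4.4% on darbepoetin alfa in an earlier study. What is at stake is whether one descriptive safety count is complete, not any efficacy conclusion.

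**Working it through.** The plan states no figure on this point, so the check is a count of the Appendix E lists.

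**List sizes.** Thrombosis 34; the broader device/shunt list 18; Device/shunt thrombosis 10; Seizure 7; Stroke 11; Sepsis 17. Total rows: 34 + 18 + 10 + 7 + 11 + 17 = 97.

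**Distinct terms.** Start with the 34 Thrombosis terms. The 18-term list adds 13, the 10-term list adds 2 more, Seizure adds 7, Stroke adds 3 and Sepsis adds 17: 34 + 13 + 2 + 7 + 3 + 17 = 76.

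**Make-up of the 34 Thrombosis terms.**

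| Group | Terms |
|---|---|
| Cerebral infarction or stroke, two of them embolic | 8 |
| Device, fistula, graft, shunt or access-site thrombosis | 7 |
| Myocardial infarction | 2 |
| Venous thrombosis or thrombophlebitis | 10 |
| Arterial, intracardiac or unspecified thrombosis | 7 |
| Total | 34 |

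The ten venous terms are deep vein, subclavian vein, brachiocephalic vein, vena cava, jugular vein, venous, pelvic venous and venous limb thrombosis, plus thrombophlebitis and superficial thrombophlebitis.

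**Search for pulmonary embolism.** Among the 76 distinct terms, those containing *embol* or *pulmon* are Embolic cerebral infarction and Embolic stroke only. Pulmonary embolism occurs in none of the six lists. No redaction mark or visible gap falls inside them.

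**Effect on a subject count.** Let N34 be the number of subjects with at least one of the 34 terms. With the extra term, N35 = N34 + (subjects with pulmonary embolism and none of the 34 terms). A subject who has both a deep vein thrombosis and a pulmonary embolism is already in N34, so only pulmonary embolism without another listed event is lost. The documents give no figure for that group. Protocol Table 2 shows only terms at 5% or more in vadadustat subjects, and pulmonary embolism is not among them.

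**The case against.** The strongest reply has four parts.

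*The SAP contradicts nothing.* The protocol leaves the AESI undefined, and an eligibility criterion does not define a safety grouping. That is right. Exclusion 13 shows only that the protocol thinks of the two conditions together. The point is one of completeness, not of conflict between documents.

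*Using external queries unmodified is legitimate.* It is, and the SAP is open about their source. Why that source omits the term cannot be checked here. This is a reason to keep the borrowed list, not a reason to let it stand alone as the protocol's AESI.

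*The event is not hidden.* This also stands. SAP section 6.12.1 tabulates all treatment-emergent events by preferred term, with separate serious and fatal tables, and states "A by-subject listing of all TEAEs will be provided".

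*Other documents may cover it.* SAP section 1 places table specifications in separate shells that are not available here, and the contents of the MedDRA queries named in Appendix E cannot be checked from the documents. If one of those queries did pick up pulmonary embolism, it would be presented under that query's topic, not under thrombosis.

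A reader might infer more than the documents support:

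- That thrombotic events has no usable definition, or that the analyst must choose among three lists with thrombosis in the title. The Thrombosis heading is a plain match by name, and Appendix E presents all its lists, so no choice is forced.
- That the 10-term device list ought to sit inside the 18-term list headed "Device/shunt thrombosis/occlusion/malfunction/Stenosis". Four of its terms do not, but nothing in the SAP says the lists should nest. They are separate queries.

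**Conclusion.** The omission is real but small. Followed as written, the lists count a deep vein thrombosis under a thrombotic topic and a pulmonary embolism under none. The consequence is confined to a descriptive AESI table, on which no hypothesis test, margin or primary safety total depends. It would be wrong to conclude that pulmonary embolisms go unreported.

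This rests on two assumptions: that the Thrombosis list is the grouping meant for the protocol's AESI, and that the table shells do not already add the term. The number of subjects affected cannot be estimated from the documents.

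**What to change.** Before database lock, define the protocol's thrombotic-events AESI in Appendix E as the Thrombosis list plus Pulmonary embolism (34 + 1 = 35 terms), and label the table as that AESI. Keep the borrowed 34-term list unchanged as a supplementary table. Making the change before lock avoids any suggestion that the term was added after seeing counts by arm.

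The cost is a line or two in Appendix E and one extra grouping in the adverse-event programming. The downside is that the count may be slightly higher and will not match the borrowed query, which is why that query is kept alongside.

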This is particularly relevant in the current medical and regulatory climate given the accumulating study findings that resulted in the FDA revising the prescribing information for the currently marketed ESAs. These study results indicate an increased risk of death and adverse CV events, such as stroke and HF, particularly when using ESAs to achieve a higher Hb concentration. In the US, the mortality and CV risks associated with ESAs are outlined in a black-box warning in the prescribing information of ESAs, with a recommendation to use the lowest dose possible to avoid transfusions. While no similar major warnings exist in the European Union (EU) Summary of Product Characteristics (SmPC), there is caution suggested with use of ESAs, and recommendation to keep Hb levels below 12.0 g/dL. Clinical practice guidelines (Locatelli 2013) recommend that risk factors for stroke and malignancy should also be taken into account when making treatment decisions to use ESAs for the treatment of anemia.

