Medical Diagnoses – Whenever possible, a medical diagnosis term should be used to report AEs instead of signs and symptoms due to a common etiology, as determined by qualified medical study staff. For example, pneumonia should be the reported AE term, instead of fever and dyspnea, when the diagnosis has been established. Signs and symptoms should be reported as event terms only when the medical diagnosis remains unknown, and revised to a medical diagnosis term once it has been established.

Procedures – Diagnostic and therapeutic non-invasive and invasive procedures, such as surgery, should not be reported as AEs. However, the medical condition for which the procedure was performed should be reported if it meets the definition of an AE. For example, an acute appendicitis that begins during the AE reporting period should be reported as the AE and the resulting appendectomy noted under ‘Comments’.

Pre-planned therapeutic procedures not associated with a new medical condition or worsening pre-existing condition should not be reported as AEs.

Device related events (failures/malfunctions) should not be reported as AEs; however, the etiology or complication associated with the device failure/malfunction should be reported if it meets the definition of an AE.

Pre-existing Conditions – In this study, a pre-existing condition (i.e., a disorder present before the AE reporting period started and noted on the pretreatment medical history/physical

examination form) should not be reported as an AE unless the condition worsens or episodes increase in frequency during the AE reporting period.

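### The Stroke AESI list names bleeding in only two of its 11 terms, so an intracranial bleed coded to another preferred term would be left out of the descriptive Stroke row

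*SAP*

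**What the plan says.** SAP Appendix E opens with "The following items will be presented as AESI". It first gives six topics defined by dictionary groupings. It then introduces a table of further topics with the statement "Adverse event preferred terms used in key queries from FDA briefing document for Roxadustat are listed below". Stroke is one of the topics in that table.

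The Stroke entry has 11 preferred terms. They include "Cerebellar infarction", "Cerebrovascular accident", "Haemorrhagic stroke" and, as the last entry, "Brain stem haemorrhage". Nothing in the entry refers to a standardised MedDRA query (SMQ), a higher-level term or further terms to be added.

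SAP section 6.12.1 calls for a summary by SOC and PT of the AESIs listed in Appendix E. The same section calls for summaries of all TEAEs, treatment-emergent SAEs and fatal TEAEs by SOC and PT. It also calls for a by-subject listing that carries the verbatim term.

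Protocol section 5.2 describes ESA trial results that point to an "increased risk of death and adverse CV events, such as stroke and HF". Protocol section 9.11.1.1 tells sites that, where possible, "a medical diagnosis term should be used to report AEs instead of signs and symptoms".

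**The concern.** A row labelled Stroke will be read as a count of all strokes. This one is built term by term, and its cover is uneven. An infarct in the cerebellum is counted, but a bleed in the cerebellum has no term of its own on the list. It is counted only if it happens to be coded to one of the general terms.

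Stroke is named in the protocol's rationale as a risk of ESAs, and worsening of hypertension is itself an AESI. A reader of the safety section may therefore look to this row for a complete count. If bleeds coded by site are missing, the row is too low, and the shortfall falls on one type of stroke.

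**Working it through.** The plan gives no figure to reproduce here. The check is a reading of the lists, followed by an illustration of size.

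**Step 1: sort the 11 Stroke terms (SAP Appendix E).**

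| Kind | Terms | Count |
|---|---|---|
| Also the first eight terms of the Thrombosis topic | Cerebral infarction, Embolic cerebral infarction, Ischaemic stroke, Cerebellar infarction, Lacunar stroke, Embolic stroke, Brain stem stroke, Lacunar infarction | 8 |
| Type not specified | Cerebrovascular accident | 1 |
| Bleeding named | Haemorrhagic stroke, Brain stem haemorrhage | 2 |

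8 + 1 + 2 = 11. Beyond what Thrombosis already holds, the Stroke topic adds three terms, and two of those three are the bleeding terms.

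**Step 2: compare by site.**

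| Site | Infarct or stroke term listed | Bleeding term listed |
|---|---|---|
| Brain stem | yes | yes |
| Cerebrum | yes | no |
| Cerebellum | yes | no |
| Subarachnoid or intracranial, unspecified | not applicable | no |

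A search of the other Appendix E topics for a cerebral, cerebellar, subarachnoid or intracranial haemorrhage term finds none. The list runs without a break or redaction mark from Stroke to the sepsis topic, so the gap does not look like text lost in extraction.

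**Step 3: ask whether the general term absorbs a bleed at a named site.** The list carries a brain stem bleed beside the general haemorrhagic term. If the general term took in bleeds at named sites, that entry would be redundant. This suggests that such a bleed can be coded to its own term. It remains an inference, because the documents do not set out which haemorrhage terms the dictionary holds or how sites will word these events.

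**Step 4: illustrate the size.** None of the three inputs below is in the documents.

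- Exposure: 360 subject-years. For scale, 450 planned subjects over a full 52 weeks would give about 450 subject-years, and 360/450 = 0.80 of that.
- Stroke rate: 2 to 4 per 100 subject-years.
- Share of strokes that are bleeds coded to an unlisted term: 10% to 30%.

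Strokes: 360 × 0.02 = 7.2 to 360 × 0.04 = 14.4.

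Missed: 7.2 × 0.10 = 0.72 to 14.4 × 0.30 = 4.32 over all three arms. Divided evenly by three, that is about 0.2 to 1.4 per arm.

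**The case against.** The strongest reply is that the list is a declared copy. The SAP says where the terms come from and does not claim to count every intracranial bleed. Comparability with the other product is a plausible reason for copying it, and a wider list would lose that. The source cannot be consulted here, so it is unknown whether the gap was in the source or arose in copying. This stands, and it is why the copied list should be kept. It does not settle what a row headed only Stroke will be taken to mean.

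A second reply is that the step from an unlisted term to an uncounted event depends on coding. The two general terms on the list are themselves diagnoses, so the protocol's request for a diagnosis does not push every bleed to a term for its site. This also stands, and the point is conditional on the coding. A reader might infer that most brain bleeds would be missed; the documents do not support that.

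A third is that nothing is lost from the report. Each such event appears by arm in the TEAE table, in the serious and fatal event tables where it qualifies, and in the listing. A reader might infer that the trial could not show a difference in brain haemorrhage between arms. That is wrong, since only the grouped subtotal is affected. A Stroke topic pools both types in any case, so it would not isolate haemorrhage even if complete.

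Finally, Stroke is not among the protocol's AESIs (Protocol sections 3.5.3 and 9.11.8), where the nearest item is thrombotic events. Nor does it break a rule that Appendix E follows elsewhere. Of the six topics above the table, five use SMQs and adrenal disorder uses higher-level terms, but every topic in the table is a list of preferred terms, as Stroke is. It would be wrong to present Stroke as the one exception.

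**Conclusion.** The point holds in a limited form. The Stroke topic is a closed list with two bleeding terms and no bleeding term for the cerebrum, cerebellum or subarachnoid space. If a bleed is coded to such a term, the Stroke row is understated by that event.

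This affects one descriptive safety row. No endpoint, hypothesis test or stopping rule uses it, and the primary analysis is untouched. The number missed cannot be derived from the documents. The illustration of 0.7 to 4.3 events over all arms rests wholly on the assumed exposure, stroke rate and bleed share, and at its low end it is less than one event. The importance is low, but so is the cost of putting it right.

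**What to change.** Before database lock, make two changes to Appendix E and the matching programming list:

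1. Keep the 11-term list unchanged and label its row by its source, so that comparison with the other product remains possible.
2. Add a second Stroke row that contains the same terms plus the cerebral, cerebellar, intracranial and subarachnoid haemorrhage preferred terms in the MedDRA version used. Alternatively, define the second row by dictionary groupings for haemorrhagic and ischaemic central nervous system vascular events, in the manner of the six topics above the table.

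No new data are needed. The cost is one extra summary row, with a slightly broader group that does not match the other product's query. Settling the terms before lock matters because the trial is open-label, and terms added once events by arm are known would be open to challenge.
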